6.2.1 Analysis of Injection pain

For each comparator PN, a two-sided 95% confidence intervals will be calculated for the average rating. A modeling approach including data from all pairs of injections (all comparator PN included) will be used to analyze the data and estimate average ratings for each comparator PN adjusting for the pair order effect, BD order effect within pair (due to the often-observed bias towards favoring the last pen needle used in a pair), abdomen site effect, comparator PN effect and random subject effect. The interaction of PN and clinical site will be verified. If the interaction is significant, multiple comparisons for site difference by each PN will be conducted and results will be presented by site for PNs with significant site difference. If the interaction is not significant, it will be dropped from the model and clinical site will be included as main effect. If the site difference is significant, results will be presented by site for each PN. Otherwise, the site effect will be dropped from the model. Results will be tested for non-inferiority, followed by superiority:

- If the lower bound of the CI is > -10mm, we can conclude in non-inferiority.
- If the lower bound of the CI is > 0mm, we can conclude in superiority.

```
> ## Example for estimated pen needle subgroup means (Site effect not significant)
> ## if the lower CL is > -10, non-inferiority is satisfied
> ## if the lower CL is > 0, superiority is satisfied
> library(emmeans)
> emmeans(model.fit, ~Comparator)
```

Comparator	emmean	SE	df	lower.CL	upper.CL
Artsana 33G	26.87836	5.747502	140.26	15.515420	38.24129
Artsana 34G	20.09732	7.841233	139.57	4.594362	35.60027
Simple Diagnostics	22.40372	6.075449	140.25	10.392416	34.41502

Degrees-of-freedom method: kenward-roger Confidence level used: 0.95

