### 13.3 Statistical Methods

Descriptive statistics (number of observations, mean, and standard deviation, minimum and maximum) will be calculated and presented for all quantitative responses. Frequency tables with number of observations, percentage of total and 95% confidence interval (score method) for the percentage (as applicable) will be created for discrete responses.

Analysis for relative VAS pain: For each comparator PN, a two-sided 95% confidence interval will be calculated for the average rating. A modeling approach may be used to adjust for the pair order effect, BD order effect within pair (due to the often-observed bias towards favoring the last pen needle used in a pair), abdomen site effect and random subject effect. Results will be tested for non-inferiority, followed by superiority:

If the lower bound of the CI is  $> -10\text{mm}$ , we can conclude in non-inferiority  
If the lower bound of the CI is  $> 0\text{mm}$ , we can conclude in superiority

Analysis for thumb force via 5-point Likert scale: For each comparator PN, the responses will be converted to ratings of  $-2 - 2$  (where positive ratings favor BD) and a two-sided 95% confidence interval will be calculated for the average rating. A modeling approach may be used to adjust for the pair order effect, BD order effect within pair, abdomen site effect and random subject effect. Results will be tested for superiority:

If the lower bound of the CI is  $> 0$ , we can conclude in superiority

Responses will also be converted to 3 categories: favoring comparator (negative ratings), no difference (0 ratings) and favoring BD Nano™ PRO (positive ratings) and the difference in percentage of responses with a preference for BD vs each comparator needle calculated, adjusting for the “no preference” category.

Analysis for needle bending and leaking: analysis will be performed using a binary logistic regression with random subject effect and fixed pen needle effect, pair order effect, PN order effect within pair and abdomen site effect. The average difference in percentage of occurrence with BD PN and each comparator PN will be calculated with 95% confidence interval and assessed for statistical significance. The upper bound of the confidence interval will be compared to 0: superiority will be concluded given that the upper bound of the 95% confidence interval for the difference in proportions is  $< 0\%$ .

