2.5.2 Secondary Objectives

- The BD Nano[™] PRO will be evaluated for superiority vs each comparator for leakage, injection force, and bending.
- If the BD Nano[™] PRO demonstrates non-inferiority for injection pain for the Primary Objective, compare the BD Nano[™] PRO vs each comparator for superiority.

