6.2 Analysis Method

This section provides a detailed description of the statistical analysis that will be performed in this study.

Unless otherwise stated, all the statistical tests are two-sided at a significance level of 5%.

Summary statistics (number of observations, mean, 95% CI for mean, median, standard deviation and range) for all quantitative responses will be presented in tables. Frequency tables with number of observations, percentage of total will be created for all discrete responses. If a modeling approach is applied, the fitted mean with 95% CI will be presented in tables.

Bar plots may be provided for some responses.

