6.2.3 Analysis of Needle Bending and Leakage

If there is a sufficient number of occurrences for a modeling approach, analysis will be performed using a binary logistic regression with random subject effect and fixed pen needle type effect, pair order effect,

DBC-18PENDL02

PN order effect within pair and abdomen site effect. The interaction of PN and clinical site will be verified. If the interaction is significant, multiple comparisons for site difference by each PN will be conducted and results will be presented by site for PNs with significant site difference. If the interaction is not significant, it will be dropped from the model and clinical site will be included as main effect. If the site difference is significant, results will be presented by site for each PN. Otherwise, the site effect will be dropped from the model. The average difference in percentage of occurrence with BD PN and each comparator pen needle will be calculated with 95% confidence interval and assessed for statistical significance. The upper bound of the confidence interval will be compared to 0: superiority will be concluded given that the upper bound of the 95% confidence interval for the difference in proportions is < 0%.

If a modeling approach cannot be applied, a proportion test will be used to detect the difference in percentage of occurrence between sites for each PN. If there is no significant difference, the difference in percentage of occurrence with BD PN and each comparator pen needle will be calculated with 95% confidence interval (Score method) and assessed for statistical significance.

PNemmeanSEdfasymp.LCLasymp.UCLBD Nano0.0794299813925529Inf-2729353527293535Artsana 33G0.079425958632818Inf-1692001316920013Artsana 34G0.0794449111568566Inf-2267397322673973Simple Diagnostics0.0794080312153341Inf-2382011023820111

Results are given on the logit (not the response) scale. Confidence level used: 0.95

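### For bending and leakage, the SAP's fallback without a model calculates the BD-minus-comparator difference only if a 5% site test is non-significant, and gives no rule for a significant result

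*SAP*

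**What the plan says.** SAP 6.2.3 gives two routes for bending and leakage.

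- **Model route.** If events are numerous enough (no threshold is given), a logistic regression with a random subject effect is fitted. A significant site finding leads to by-site presentation. The BD-minus-comparator difference and its superiority rule (upper 95% limit below 0) carry no site condition.
- **Fallback route.** Otherwise, "a proportion test will be used to detect the difference in percentage of occurrence between sites for each PN". The next step is: "If there is no significant difference, the difference in percentage of occurrence with BD PN and each comparator pen needle will be calculated", with a 95% score interval. The rule ends there. It does not say what follows if sites differ, or whether a site difference in any of the four needles, or only in the two being compared, stops the calculation.

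SAP 6.2 sets tests at two-sided 5% unless otherwise stated, and 6.2.3 states no other level for the site test.

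Two other places expect the comparison to be made. Protocol 13.3 has only the model route and no site test: "The average difference in percentage of occurrence with BD PN and each comparator PN will be calculated with 95% confidence interval". SAP 2.5.2 says that BD Nano PRO "will be evaluated for superiority vs each comparator for leakage, injection force, and bending".

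For pain, SAP 6.2.1 sends results to by-site presentation after a significant interaction ("results will be presented by site for PNs with significant site difference") or a significant site main effect ("If the site difference is significant, results will be presented by site for each PN").

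**The concern.** The fallback makes a formal secondary comparison depend on a preliminary test of a different question. Whether sites differ in their bending or leakage rate says little about whether BD Nano PRO bends or leaks less than a comparator, since every subject uses all four needles at the same site. Yet a significant site test for one needle leaves the analyst without an instruction. Either the comparison is not produced, or someone chooses after seeing the site results among a pooled difference, by-site differences or some other analysis. Bending and leakage are two of the secondary superiority objectives, each assessed against three comparators.

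**Working it through.** **The plan's own figures.** The plan gives no error rate for the site test. Its leakage power (Protocol Table 1: 90%, 98%, >99%) refers to the all-site comparison of 266 comparator with 798 BD injections. A pooled two-proportion formula gives 98.4%, 99.8% and >99.9%. Drawing the rates from beta distributions around the earlier counts gives 93.5-94.5%, 98.5-98.8% and >99%. The statement of more than 90% is met. The exact 90% for Artsana 33G is not matched, and the simulation code is not in the documents. None of these figures allows for a site condition.

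**Inputs.** Leakage rates from SAP 3: BD 3/297, Artsana 33G 19/296, Comfort EZ 25/299, Artsana 34G 66/298. Injections: 798 BD and 266 per comparator. Test level 5%. Assumed: no true site effect, 2 or 3 equal sites (the design is multi-center but the number is not given), and independent injections.

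**Nominal rates.** Two needles: 1 - 0.95^2 = 9.75%. Four needles: 1 - 0.95^4 = 18.5%.

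**Leakage rates, 2 sites, uncorrected chi-square.** Enumerating the binomial outcomes (399 BD and 133 comparator injections per site) gives these chances of a significant site test: BD 4.37%, Artsana 33G 4.86%, Comfort EZ 5.05%, Artsana 34G 5.06%.

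- Either of two, Artsana 33G: 1 - 0.9563 x 0.9514 = 9.0%. The same step gives 9.2% for each of the other two comparators.
- Any of four: 1 - 0.9563 x 0.9514 x 0.9495 x 0.9494 = 18.0%.

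**Other settings.**

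| Setting | Either of two | Any of four |
|---|---|---|
| Leakage, 3 sites, uncorrected (simulated) | 8.9-9.1% | 17.6% |
| Leakage, 2 sites, Yates | 4.3-5.2% | 10.2% |
| Leakage, 2 sites, Fisher | about 4-5% | about 10% |
| Bending, uncorrected | 6-9% | 11-18% |
| Bending, 2 sites, Yates | 0.6-5% | 1-9% |

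The documents give no bending rates. The bending rows assume 0.5-2% for BD and 1-5% for comparators. Injections are clustered within subjects, so positive within-subject correlation would raise all these rates; this was not quantified.

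**How plausible is the fallback?** Expected leakage events at the SAP's rates:

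- BD: 798 x 3/297 = 8.1
- Artsana 33G: 266 x 19/296 = 17.1
- Comfort EZ: 266 x 25/299 = 22.2
- Artsana 34G: 266 x 66/298 = 58.9

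The total is about 106 events in 1,596 injections. One model covers all four needles, so at these rates the model is the likelier route for leakage. For bending no such count can be made.

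**The case against.** **The percentages are conditional.** They apply only once the fallback is in use, and how often that happens cannot be computed because no event threshold is given. The leakage figures use rates at which the model would probably be fitted. The 18% also needs the broadest reading, that any of the four needles blocks every comparison. Where events are sparse, a corrected test can bring the figure below 1%. All of this stands. It limits the size of the problem but does not supply the missing branch.

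**The gap withholds a claim and does not itself create a false one.** This stands too. SAP 6.2.4.2 gives the score interval for needle breaking without a condition and treats site as something to verify, which suggests that the site test was meant as a check. That supports the fix: the intended rule is probably unconditional, but the fallback says otherwise.

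**A stronger reading about pain is tempting.** A reader might infer that a significant site test also takes the primary decision away from the all-site interval. The only worked call in SAP 6.2.1 is labelled "Example for estimated pen needle subgroup means (Site effect not significant", and the power of a single site would be much lower: Phi(10/(50/sqrt(266/k)) - 1.96) is 0.904 for all sites (k = 1), 0.636 with 2 sites and 0.469 with 3. The documents do not support that inference. SAP 6.2.1 opens with one interval per comparator, SAP 2.5.1 sets one criterion per comparator, Protocol 13.3 has no site test, and example Tables 3 and 5 show one conclusion per comparator. By-site presentation is a reporting step. On that reading nothing is lost for pain.

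**Conclusion.** The point holds for the SAP 6.2.3 fallback only. As written, a significant site test leaves bending or leakage without a defined superiority comparison, which conflicts with Protocol 13.3 and SAP 2.5.2. That follows from the text and needs no assumption.

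The size does rest on assumptions: fallback in use, no true site effect, 2 or 3 equal sites, independent injections. At the SAP's leakage rates a comparison is withheld by chance in about 9% of trials (either needle blocks) to 18% (any of four blocks) with an uncorrected test, and in about 4-5% and 10% with Yates or Fisher at 2 sites. For bending, the more plausible use, the range runs from under 1% to about 18%, depending on the assumed rates, the test and the reading. These are not overall probabilities for the trial. The pain section contains no error; a sentence there would be clarification only.

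**What to change.** In the SAP 6.2.3 fallback, replace the condition with wording such as:

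> For each comparator, the BD-minus-comparator difference in the proportion of injections with the event, over all sites, and its 95% score CI will be calculated and will decide superiority whether or not sites differ. Site tests and by-site results are supportive.

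This also removes the question of which needles' site tests count.

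Optional: state in SAP 6.2.1 that the all-site adjusted mean and its two-sided 95% CI decide pain non-inferiority and superiority whatever the site tests show.

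The cost is SAP wording only. No data, procedures or sample size change, and the site tests and by-site tables remain as supportive output.

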6.2.1.1 Additional analysis

Given that there is no significant site effect and no significant difference between any comparator PNs, data from DBC-18PENDL02 and DBC-18PENDL01 will be combined for analysis. An overall result combining all comparators in the two studies will be presented.

6.2.2 Analysis of Injection force

For each comparator PN, the responses in 5-point Likert scale will be converted to ratings of -2 to 2 (where positive ratings favor BD, see Section 6.1.3) and a two-sided 95% confidence interval will be calculated for the average rating. A modeling approach including data from all pairs of injections (all comparator PN included) will be used to analyze the data and estimate average ratings for each comparator PN adjusting for the pair order effect, BD order effect within pair (due to the often-observed bias towards favoring the last pen needle used in a pair), abdomen site effect, comparator PN effect and random subject effect. The interaction of PN and clinical site will be verified If the interaction is significant, multiple comparisons for site difference by each PN will be conducted and results will be presented by site for PNs with significant site difference. If the interaction is not significant, it will be dropped from the model and clinical site will be included as main effect. If the site difference is significant, results will be presented by site for each PN. Otherwise, the site effect will be dropped from the model.

If the lower bound of the CI for the average rating is > 0 mm, we can conclude in superiority.

Responses will also be converted to 3 categories: favoring comparator pen needle (negative ratings), no difference (0 ratings) and favoring BD NanoTMPRO (positive ratings) (see Section 6.1.3). The difference in percentage of responses with a preference for BD Nano vs each comparator pen needle will be calculated by Bayesian approach, adjusting for the "no preference" category.

6.2.2.1 Additional analysis

Given that there is no significant site effect and no significant difference between any comparator PNs, data from DBC-18PENDL02 and DBC-18PENDL01 will be combined for analysis. An overall result combining all comparators in the two studies will be presented.

6.2.3 Analysis of Needle Bending and Leakage

If there is a sufficient number of occurrences for a modeling approach, analysis will be performed using a binary logistic regression with random subject effect and fixed pen needle type effect, pair order effect,

DBC-18PENDL02

PN order effect within pair and abdomen site effect. The interaction of PN and clinical site will be verified. If the interaction is significant, multiple comparisons for site difference by each PN will be conducted and results will be presented by site for PNs with significant site difference. If the interaction is not significant, it will be dropped from the model and clinical site will be included as main effect. If the site difference is significant, results will be presented by site for each PN. Otherwise, the site effect will be dropped from the model. The average difference in percentage of occurrence with BD PN and each comparator pen needle will be calculated with 95% confidence interval and assessed for statistical significance. The upper bound of the confidence interval will be compared to 0: superiority will be concluded given that the upper bound of the 95% confidence interval for the difference in proportions is < 0%.

If a modeling approach cannot be applied, a proportion test will be used to detect the difference in percentage of occurrence between sites for each PN. If there is no significant difference, the difference in percentage of occurrence with BD PN and each comparator pen needle will be calculated with 95% confidence interval (Score method) and assessed for statistical significance.

PNemmeanSEdfasymp.LCLasymp.UCLBD Nano0.0794299813925529Inf-2729353527293535Artsana 33G0.079425958632818Inf-1692001316920013Artsana 34G0.0794449111568566Inf-2267397322673973Simple Diagnostics0.0794080312153341Inf-2382011023820111

Results are given on the logit (not the response) scale. Confidence level used: 0.95

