## 3.0 STUDY DESIGN

### 3.1 Overall Study Design

This is a subject partially blinded, block randomized, prospective, single-visit, multi-center study to compare user experiences with BD Nano™ PRO pen needle vs. three (3) thinner commercially available comparator pen needles (Artsana Insupen Extr3me 33G, Artsana

Insupen Extr3me 34G and the Simple Diagnostics Comfort EZ™ 33G Pen Needles). The study will include up to 146 study subjects having Type 1 or Type 2 diabetes.

Study conduct will consist of one 60 to 120 minute Site visit in which pre-set doses of saline will be abdominally delivered by Subjects via a reusable insulin pen device. All pen needles will be attached by Study Staff and pen needle outer cover and inner shield will be removed for subjects. Subjects are to perform 12 injections into the abdomen (6 pairs of injections). Pairs of injections will be evaluated and each pair will contain one BD Nano™ PRO and one comparator pen needle. Within the 12 injections, each comparator will be injected twice, therefore each subject will experience 2 of each of the following pairs:

BD Nano™ PRO pen needle vs Artsana Insupen Extr3me 4mm x 33G x 2

BD Nano™ PRO pen needle vs Artsana Insupen Extr3me 3.5mm x 34G x 2

BD Nano™ PRO pen needle vs Simple Diagnostics Comfort EZ™ 4mm x 33G x 2

Subjects will not see pen needle labels or be informed which pen needle is being used to inject. The BD Nano™ PRO has a distinct configuration and subjects will most likely notice the difference vs the comparators. Subjects will not be informed of the BD's or the comparator's pen needle brand, length or gauge.

The pen needle order within the pairs of injections will be randomized for each subject and the pairs will be randomized to various abdominal injection sites within each subject.

Besides being informed of the requirement to insert the pen needles 'straight-in' (perpendicular), subjects will be instructed to use their usual injection technique.

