#### 13.1 Sample Size Determination

**Pain:** Assuming the SD for relative VAS is ~50mm (based on DBC-17NUCLS07), a sample size of 266 pairs per each comparator has >90% power of passing a -10mm NI criteria, assuming no true difference in pain (based on a 2-sided 95% CI for the mean).

**Leakage:** Based on previous study data (BDT-2P00116) where leakage  $\geq 1.5U$  was observed in 66/298 (22.1%) of injections performed with Artsana 34G, in 25/299 (8.4%) of injections performed with Comfort EZ 33G, in 19/296 (6.4%) of injections performed with Artsana 33G and in 3/297 (1%) of injections performed with BD Nano™ PRO, a simulation was performed (code found in SVN repository under DBC-18PENDL01\Stat\Sample Size\Bayesian prior proportion R) indicating that 798 injections with BD Nano™ PRO and 266 injections per each comparator would provide >90% power to show BD Nano™ PRO superiority to each comparator.

A 10% buffer was added (to compensate for subject attrition or unusable data), leading to a planned enrollment number of 146 subjects.

Table 1 summarizes the sample size scenario.

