2.5.3 Exploratory Objectives

No formal acceptance criterion has been established for the following objectives - time to deliver dose, total injection time, and survey responses after all injections completed.

3 Sample Size

Pain: Assuming the SD for relative VAS is around 50mm (based on DBC-17NUCLS07), a sample size of 266 pairs per each comparator has >90% power of passing a -10mm NI criteria, assuming no true difference in pain (based on a 2-sided 95% CI for the mean).

Leakage: Based on previous study data (BDT-2P00116) where leakage was greater than or equal to 1.5U was observed in 66/298 (22.1%) of injections performed with Artsana 34G, in 25/299 (8.4%) of injections performed with Comfort EZ 33G, in 19/296 (6.4%) of injections performed with Artsana 33G and in 3/297 (1%) of injections performed with BD NanoTM PRO, a simulation was performed (code found in SVN repository under DBC-18PENDL01/Sample Size/Bayesian prior proportion.R) indicating that 798 injections with BD NanoTM PRO and 266 injections per each comparator would provide >90% power to show BD NanoTM PRO superiority to each comparator. So the number of subjects needed is 133.

A 10% buffer was added (to compensate for subject attrition or unusable data), leading to a planned enrollment number of 146 subjects.

4 Intended Statistical Software

This document was generated with R version 3.5.1 (2018-07-02) and the following packages (version) were used: assertthat (0.2.0), base (3.5.1), BDbasics (0.2.4), bindr (0.1.1), bindrcpp (0.2.2), colorspace (1.3.2), compiler (3.5.1), crayon (1.3.4), datasets (3.5.1), dplyr (0.7.6), ggplot2 (3.1.1), glue (1.3.0), graphics (3.5.1), grDevices (3.5.1), grid (3.5.1), gtable (0.2.0), lattice (0.20.35), lazyeval (0.2.1), magrittr (1.5), methods (3.5.1), munsell (0.5.0), nlme (3.1.137), pillar (1.3.0), pkgconfig (2.0.2), plyr (1.8.4), purrr (0.2.5), R6 (2.2.2), Rcpp (0.12.18), reshape2 (1.4.3), rJava (0.9.10), rlang (0.2.2), scales (1.0.0), stats (3.5.1), stringi (1.1.7), stringr (1.3.1), tibble (1.4.2), tidyselect (0.2.4), tools (3.5.1), utils (3.5.1), withr (2.1.2), xlsx (0.6.1), xtable (1.8.3).

The analysis of this study will be conducted within the same environment or using more recent versions.

5 Data

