6.2.4.2 Needle Breaking

The number and proportion of needle breaking occurrence for each pen needle type will be summarized. In addition, a 95% confidence interval for difference in proportions between BD Nano PN and each comparator PN will be calculated using the score method for independent proportions. Site effect will be verified in a similar way with needle bending.

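### The score interval for needle breakage, and by inference the no-model fallback for bending and leakage, ignores that each subject uses both needles repeatedly; its error can go either way and is small where the fallback is most likely to be used

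*SAP*

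**What the plan says.** Protocol 3.1 sets six pairs of injections per subject: "each pair will contain one BD Nano™ PRO and one comparator pen needle", and "each comparator will be injected twice". Each subject therefore contributes six BD injections and two with each comparator. SAP section 3 (Sample Size) gives 133 subjects, and Protocol 13.1 sizes leakage on "798 injections with BD Nano™ PRO and 266 injections per each comparator would provide >90% power".

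For bending and leakage, Protocol 13.3 and SAP 6.2.3 both specify logistic regression with a random subject effect. SAP 6.2.3 makes this conditional on a sufficient number of occurrences, which it does not define. If modelling is not possible, each needle is first compared between sites with a proportion test. If the sites do not differ, the BD-comparator difference "will be calculated with 95% confidence interval (Score method) and assessed for statistical significance". The Protocol has no such fallback.

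For breakage, an exploratory endpoint, SAP 6.2.4.2 gives a 95% interval for the difference "calculated using the score method for independent proportions".

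**The concern.** An independent-proportions interval takes the variance of the difference as the sum of two binomial variances. In this design that leaves out two things. Repeated injections by one subject with one needle are correlated, which adds variance. The same subjects supply both proportions, which induces a covariance that removes variance. The net effect depends on the balance between them, and the interval uses neither.

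The main model carries a subject effect; the fallback drops it. If the fallback is used, the interval decides superiority on two secondary endpoints against three comparators each, so an interval of the wrong width could produce a false claim or lose a true one.

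**Working it through.** **Inputs.** K = 133 subjects; 6 BD and 2 comparator injections each, so 798 against 266 (Protocol 13.1 and Table 1). Superiority is read from one end of a two-sided 95% interval, so nominal one-sided error is 2.5%. Planning leakage rates (Protocol 13.1): BD 3/297 = 1.01%, Artsana 33G 19/296 = 6.42%, Comfort EZ 25/299 = 8.36%, Artsana 34G 66/298 = 22.15%. The documents give no within-subject correlation and no planning rate for bending or breakage.

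**The plan's own figure.** Drawing true rates from Beta(x+1, n−x+1), then independent binomials of size 798 and 266, and declaring success when the unpooled 95% upper limit is below 0, gives power of 89.8% / 97.6% / >99.9%. Table 1 states 90% / 98% / >99%. The stated power is thus reproduced with injections treated as independent.

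**Variance at equal rates.** Let rw be the correlation between two injections by one subject with the same needle, rb that between different needles, and s² = p(1−p).

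- True variance: (s²/K)[(1+rw)/2 + (1+5rw)/6 − 2rb]
- Independence: (s²/K)(1/2 + 1/6) = (s²/K)(2/3)
- One shared subject effect (rw = rb = r): the ratio is 1 − r. For r = 0.1, 0.2, 0.3 the correct width is 0.95, 0.89, 0.84 of the independent one, and one-sided error is 1.9%, 1.4%, 1.0%. The interval is too wide.
- Needle-specific effects only (rb = 0): the ratio is 1 + 2rw. For rw = 0.1, 0.2, 0.3 the correct width is 1.10, 1.18, 1.26 times, and one-sided error is 3.7%, 4.9%, 6.1%. The interval is too narrow.

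**Very different rates.** At 1.01% against 22.15%, the two binomial variances are 0.0101 × 0.9899 = 0.0100 and 0.2215 × 0.7785 = 0.1724. Setting all three correlations to r, the added variance is 0.1724/2 + 5 × 0.0100/6 = 0.0862 + 0.0083 = 0.0945 per unit of r. The covariance removes 2 × √(0.0100 × 0.1724) = 0.0830. The net is +0.0115r, so even a fully shared correlation no longer makes the interval conservative. A simulated shared logit effect with SD 2 gave 92.4% coverage at these rates.

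**Simulated coverage.** 133 subjects, the Newcombe interval built from Wilson limits, and normal subject effects on the logit scale (assumed): shared SD 0 to 2, needle-specific SD 0 to 1.5.

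| Rates | Coverage | One-sided error |
|---|---|---|
| Equal, 5 to 22%, shared SD 2 only | up to 98.6% | 0.8 to 1.6% |
| Equal, 5 to 22%, needle-specific SD 1.5 only | down to about 89% | 4.9 to 5.8% |
| Planning rates | about 90 to 95% | – |
| Equal, 0.5 to 2% | about 94 to 98% | 1.8 to 4.3% |

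A needle-specific SD of 2 lowers the equal-rate minimum to about 87% and takes the rare-event figures somewhat below the range shown.

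With no subject effect at all, one-sided error at equal rates of 0.5 to 2% is already about 3%, so part of the excess there is not clustering.

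**After scaling by the clustered variance** (formula under the fix), coverage is about 94.6 to 95.6% at equal rates of 5 to 22% and at the planning rates. At equal rates of 0.5 to 2%, one-sided error is 2.6 to 3.7%.

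**The case against.** The strongest objection is scope. The planned analysis already handles clustering, and the score interval enters only if the model fails. At the planning rates the trial expects 798 × 0.0101 ≈ 8 BD leaks and 266 × 0.0642 ≈ 17, 266 × 0.0836 ≈ 22 and 266 × 0.2215 ≈ 59 comparator leaks, about 106 in all. That makes the model the likely route for leakage. The largest errors arise at equal rates of 5 to 22%, or roughly 40 to 175 BD events, which is hard to call too few. They also need strong needle-specific effects, for which the documents give no evidence.

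Where events are rare, the decision hardly moves. At 0.5% against 2%, superiority was declared in 57 to 58% of simulated trials unscaled and 54 to 59% scaled. At 1% against 6.4% it was 98.9 to 99.6% against 98.4 to 99.7%. Breakage has no superiority rule.

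All of this stands, and it limits the size of the point. It does not make the stated variance right for the design: the threshold for using the fallback is undefined, bending has no planning rate, and the direction of error cannot be known in advance.

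A reader might also infer that the SAP states independence for bending and leakage. It does not: 6.2.3 says only that a score method is used. The inference is reasonable, because no paired or clustered version is named, there is no subject term, and the counts are unequal (798 against 266).

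**Conclusion.** The point holds in limited form. SAP 6.2.4.2 states an interval that does not fit the design, and the fallback in 6.2.3 by inference uses the same one. Coverage can fall on either side of 95%: about 89 to 98.6% at equal rates of 5 to 22%, about 90 to 95% at the planning rates, and about 94 to 98% in the rare-event range where the fallback is most likely to apply. The effect on the superiority decision in that range is small.

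A reader might conclude that the intervals are simply wrong, or that false superiority claims on bending and leakage are to be expected. The documents do not support that. They give no correlation, a shared subject effect with similar rates makes the interval conservative, and the fallback is conditional. The random-subject logistic model and the primary pain analysis are not touched.

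The figures assume logit-normal subject effects with the SDs given, the Newcombe form of the score interval, and 133 complete subjects.

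**What to change.** In the SAP 6.2.3 fallback and in 6.2.4.2, name an interval that accounts for subject clustering. Either of these would serve:

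- a bootstrap that resamples whole subjects; or
- the score interval with each half-width multiplied by √(V_sub / V_ind). V_sub is the sample variance, across subjects, of the BD proportion (of 6) minus the comparator proportion (of 2), divided by the number of subjects. V_ind is p_B(1−p_B)/n_B + p_C(1−p_C)/n_C.

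Revert to the unscaled interval only when there are no events. The coverage figures quoted above after correction are for the scaled interval; they do not cover the bootstrap.

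The cost is SAP wording and a few lines of code on data already collected. One-sided error stays slightly above nominal, at about 3 to 3.7%, when events are rare. Scaling can also raise error where the unscaled interval was conservative: at equal rates of 2% with a shared SD of 2, from 2.2% to 3.3%.
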